10.3.4 Method of Assigning Patients to Treatment Groups

Patients will be randomized on the last day of the open-label run-in period (Day 0) to either Treatment Sequence 1 or 2, in a 1:1 ratio. Based upon the Treatment Sequence assigned, patients will receive either amifampridine phosphate or placebo in Period 1 and the other treatment in Period 2. A stabilization period using open-label amifampridine phosphate will occur between switches of amifampridine phosphate and placebo. IP will be administered under double-blind conditions for each Sequence.

The randomization code will be provided by Catalyst or designee to the site Pharmacist. Details will be included in the Pharmacy Manual.

 Catalyst <small>pharmaceuticals</small>	CMS-001 Version Amendment 5	Page 48
---	--------------------------------	---------

10.3.5 Selection of Doses Used in the Study

The amifampridine phosphate dose is 10 mg to 80 mg total daily dose, given in 2 to 4 divided doses, with no single dose >15 mg in patients up to 16 years of age or >20 mg in patients >16 years of age. Safety of a single maximum dose of 20 mg is based on completed animal and *in vitro* pharmacology, PK, and toxicology studies.

10.3.6 Blinding

This is a double-blind study where both the patients (parent/guardian/caregiver) and investigator will be blinded to treatment assignment.

10.3.7 Treatment Compliance

Patients will be instructed to return all IP containers and remaining study medication at each study visit. Patient compliance with the dosing regimen will be assessed by reconciliation of the used and unused IP. The quantity dispensed, returned, used, lost, etc., must be recorded on the medication dispensing log provided for the study.

10.3.8 Investigational Product Accountability

The study site pharmacy is responsible for maintaining accurate records (including dates and quantities) of IP(s) received, patients to whom IP is dispensed (patient-by-patient dose specific accounting), IP returned, and IP lost or destroyed. The investigator, study site pharmacy or designee must retain all unused or expired study supplies until the study monitor (on-site CRA) has confirmed the accountability data.

10.3.9 Return and Disposition of Clinical Supplies

Unused IP must be kept in a secure location for accountability and reconciliation by the study monitor. The investigator or designee must provide an explanation for any destroyed or missing IP or study materials.

Unused IP may be destroyed on site, per the site's standard operating procedures, but only after Catalyst has granted approval for drug destruction. The monitor must account for all IP in a formal reconciliation process prior to IP destruction. All IP destroyed on site must be documented. Documentation must be provided to Catalyst and retained in the investigator study files. If a site is unable to destroy IP appropriately, the site can return unused IP to Catalyst upon request. The return of IP or IP materials must be accounted for on a Study Drug Return Form provided by Catalyst.

All IP and related materials should be stored, inventoried, reconciled, and destroyed or returned according to applicable regulations and study procedures.

 Catalyst <small>pharmaceuticals</small>	CMS-001 Version Amendment 5	Page 49
---	---------------------------------------	----------------

10.4 Prior and Concomitant Medications

All prescription and over-the-counter medications and herbal and nutritional supplements taken by a patient for 14 days before the Screening visit will be recorded on the designated case report form (CRF).

The investigator may prescribe additional medications during the study, as long as the prescribed medication is not prohibited by the protocol. In the event of an emergency, any needed medications may be prescribed without prior approval, but the Medical Monitor must be notified of the use of any contraindicated medications immediately thereafter. Any concomitant medications added or discontinued during the study should be recorded on the CRF.

Medications prohibited during the study are listed in [Table 5](#).

Table 5. Medications Prohibited During Study

Any investigational product (other than amifampridine phosphate) or an investigational medical device within 30 days before Screening

The following medicinal products should be used with caution in patients taking amifampridine phosphate:

Medicinal products known to cause cardiac QT prolongation

Medicinal products known to lower epileptic threshold

Medicinal products with atropinic effects

The concomitant use of amifampridine phosphate and medicinal products with atropinic effects may reduce the effect of both active substances and should be taken into consideration. Medicinal products with atropinic effects include tricyclic anti-depressants, most H1 atropinic anti-histamines, anticholinergic, anti-Parkinson medicinal products, atropinic antispasmodics, disopyramide, phenothiazine neuroleptics and clozapine.

Medicinal products with cholinergic effects

The concomitant use of amifampridine phosphate and medicinal products with cholinergic effects (e.g. direct or indirect cholinesterase inhibitors) may lead to an increased effect of both products and should be taken into consideration.

Non-depolarizing muscle relaxant acting medicinal products

 Catalyst <small>pharmaceuticals</small>	CMS-001 Version Amendment 5	Page 50
---	---------------------------------------	----------------

The concomitant use of amifampridine phosphate and medicinal products with non-depolarizing muscle relaxant effects (e.g. mivacurium, pipercurium) may lead to a decreased effect of both products and should be taken into consideration.

Depolarizing muscle relaxant acting medicinal products

The concomitant use of amifampridine phosphate and medicinal products with depolarizing muscle relaxant effects (e.g. suxamethonium) may lead to a decreased effect of both products and should be taken into consideration.

10.5 Dietary or Other Protocol Restrictions

10.5.1 Dietary Restrictions

There are no dietary restrictions for patients during any part of this study.

10.5.2 Contraception

Sexually active males and females of childbearing potential must use effective forms of contraception, such as condom for males or occlusive cap (diaphragm or cervical/vault caps) for females, during the study.

10.6 Safety Variables

Safety in this study will be determined from evaluation of AEs/SAEs, vital signs assessments, clinical laboratory assessments, ECGs, and physical examinations. Pregnancy testing is also required for females of childbearing potential. The timing of the required evaluations is described in the Schedule of Events in [Table 3](#) and in Section 13.

10.6.1 Adverse Events

The determination, evaluation and reporting of AEs will be performed as outlined in Section 11.

10.6.2 Vital Signs

Specific visits for obtaining vital signs are provided in [Table 3](#) and in Section 13. Vital signs will be measured while in a sitting position, after resting for 5 minutes, and include SBP and DBP measured in millimeters of mercury (mmHg), heart rate in beats per minute, respiration rate in breaths per minute. Weight (kg) and temperature in degrees Celsius (°C) will also be measured. Clinically significant changes from baseline will be recorded as AEs.

10.6.3 Clinical Laboratory Assessments

Specific visits for obtaining clinical laboratory assessment samples are provided in [Table 3](#) for the tests required by Protocol. The scheduled clinical laboratory tests are listed in [Table 6](#).

All abnormal clinical laboratory result pages should be initialed and dated by an investigator, along with a comment for each abnormal result indicating whether or not it is clinically significant. Any abnormal test results determined to be clinically significant by the investigator should be repeated (at the investigator's discretion) until the cause of the abnormality is determined, the value returns to baseline or to within normal limits, or the investigator determines that the abnormal value is no longer clinically significant.

Each clinically significant laboratory result should be recorded as an AE. The diagnosis, if known, associated with abnormalities in clinical laboratory tests that are considered clinically significant by the investigator will be recorded on the AE CRF.

Table 6. Clinical Laboratory Tests

Liver Function Tests	Renal Function Tests	Electrolytes	Other
Alkaline phosphatase ALT (SGPT) AST (SGOT)	Blood urea nitrogen Creatinine	Sodium Potassium Chloride Calcium	Pregnancy test, if applicable CMS genetic testing ^a

ALT, alanine aminotransferase; AST, aspartate aminotransferase; BUN, blood urea nitrogen; CMS, congenital myasthenic syndromes; SGOT, serum glutamic-oxaloacetic transaminase; SGPT, serum glutamic-pyruvic transaminase.

^a At Screening, if not previously done or available. If previously done, a copy of the CMS genetic testing results should be included in the patient's CRF.

10.6.4 Pregnancy Testing

Female patients of childbearing potential will have a serum (at Screening) or urine pregnancy test at any other time points specified in the Schedule of Events ([Table 3](#)) and in [Section 13](#).

Female patients with a positive pregnancy test at Screening do not meet eligibility criteria for enrollment.

Refer to [Section 11.4](#) for details on the reporting procedures to follow in the event of pregnancy.

10.6.5 Electrocardiogram

A standard 12-lead safety ECG (single tracing) will be recorded with the patient resting comfortably in the supine position at the time points specified in the Schedule of Events

 Catalyst pharmaceuticals	CMS-001 Version Amendment 5	Page 52
--	--------------------------------	---------

([Table 3](#)) and in Section 13. Clinically significant changes from baseline will be recorded as AEs.

10.6.6 Physical Examination

A complete physical examination will be performed at the time points specified in the Schedule of Events in [Table 3](#) and in Section 13. Complete physical examination will include assessments of general appearance as well as the following:

- Head
- Eyes
- Ears
- Nose
- Throat
- Cardiovascular
- Dermatologic
- Lymphatic
- Respiratory
- Gastrointestinal

Weight will be measured with each physical examination throughout the study. Height will be measured at screening only.

Other body systems may be examined. Clinically significant changes from baseline will be recorded as AEs.

An abbreviated physical examination may be performed as clinically indicated. The procedures and assessments for performing an abbreviated physical examination will be at the discretion of the investigator.

10.7 Efficacy Variables

The timing of required evaluation is described in the Schedule of Events in [Table 3](#) according to the sequence listed below.

Assessment	Start Time After Dose* (± 10 minutes unless otherwise specified)
SGI	40 minutes
MFM 20 or 32	after SGI
Stimulated Single fiber EMG	after MFM
Slurp test, CGI-S and CGI-I	At end of assessments

*Administration of medication represents Time 0 (minutes)

If the stimulated single fiber EMG (optional assessment) is not to be performed, then the slurp test (also optional), CGI-S and CGI-I assessments should be done following completion of the MFM.

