10.3.3 Directions for Administration

All doses of study treatment will be taken at home, except during the in-clinic study visit. If the patient takes the IP two or more times a day, then the patient should be given specific instructions on dosing relative to the time of their clinic visit to assure a dose will be given

during the in-clinic visits. A dose must be administered in the clinic in order to facilitate efficacy assessments. All safety assessments (vital signs, laboratory tests) are to be performed before the dose administered to the patient during the scheduled in-clinic visit. All efficacy assessments will be performed at standardized times relative to the dose administered in the clinic. In this case, the dose will be 40 minutes before the first efficacy assessment.

Assessment	Start Time After Dose* (\pm 10 minutes unless otherwise specified)
SGI	40 minutes
MFM 20 or 32	after SGI
Simulated Single fiber EMG [^]	after SGI
Slurp test [^] , CGI-S and CGI-I	At end of assessments

*Administration of medication represents Time 0 (minutes)

[^]Optional test

If the stimulated single fiber EMG (optional assessment) is not to be performed, then the slurp test (also optional), CGI-S and CGI-I assessments should be done following completion of the MFM.

The dose of amifampridine phosphate will be individually determined by the investigator, within the bounds of a total daily dose of 10 mg to 80 mg, divided into doses taken 2 to 4 times per day generally taken with food (e.g. breakfast, lunch, dinner, and snack before bed) as prescribed by the investigator, based on optimal neuromuscular benefit (see [Table 4](#)).

All doses of study medication will be taken orally by mouth, with the following exceptions:

- children unable to swallow tablets will have the tablets crushed and mixed with a small amount of food; and
- children with a nasogastric or gastrostomy tube will have the tablets crushed and diluted in 5 to 10 mL of water and given through the tube.

Table 4. Dosing Guidelines

	Children^a		
	Ages up to 3 Years	Ages 3 to 16 Years	Ages >16 years
Recommended starting dose	1 mg/kg/day, 3 times per day (to a maximum of 5 mg, 3 times a day)	5 mg, 3 times per day (15 mg/day total)	10 mg, 3 times per day (30 mg/ day total)
Initial dose escalation	May increase dose to 1 mg/kg, 4 times per day	May increase dose to 10 mg, 3 times per day (30 mg/day total)	May increase dose to 10 mg, 4 times per day (40 mg/day total)

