10.7.4 Stimulated Single Fiber Electromyogram

Stimulated single fiber EMG is a method to assess the integrity of the neuromuscular junction. The principle of stimulated single fiber EMG is to measure the time variability of the muscle fiber action potentials as they are generated by the discharges of the motor neuron (SFEMG using voluntary activation) versus the variability of a single muscle fiber potential (SFEMG using motor axonal stimulation). In infants, young children, or patients having difficulty in making a controlled activation, stimulated jitter analysis is preferable. From a technical standpoint, facial muscles such as the frontalis and orbicularis oculi are the easiest to record by stimulating the distal branch of the facial nerve supplying them with a monopolar needle electrode. The latter has less associated stimulation artifact and better control of the stimulating impulse. Since the recordings are made with a disposable concentric needle electrode, the term "jitter analysis" is preferred as being semantically more correct than single fiber EMG. Stimulated jitter analysis will be performed by a certified electromyographer. Local anesthetic agent will be applied to the site of needle electrode

 Catalyst <small>pharmaceuticals</small>	CMS-001 Version Amendment 5	Page 55
---	---------------------------------------	----------------

examination 30 minutes before the procedure. Not all patients can tolerate the procedure so this test is optional.

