13.2 Open-label Run-in

Patients, previously not on amifampridine phosphate treatment for CMS may visit the study site for weekly visits for up to 4 weeks throughout the run-in period for the assessments and

 Catalyst pharmaceuticals	CMS-001 Version Amendment 5	Page 62
--	--------------------------------	---------

procedures listed in [Table 3](#). Efficacy measurements will be performed during or at the end of run-in to document improvement or maintenance of optimal benefit of study drug. Additional visits or telephonic interactions are allowed as necessary.

At the end of this period (Day 0), patients must have been on a stable dose and frequency for 7 days and show at least a 20% improvement in MFM 20 or 32 (depending on the age of patient) from Day 1 of Run-in.

Patients already receiving amifampridine phosphate treatment for CMS meeting the inclusion and exclusion criteria are eligible to participate in this study. They can be randomized into Period 1 if on stable dose and frequency for 1 week before being randomized to a Treatment Sequence. Improvement of at least 20% in MFM 20 or 32 is not a requirement for these participants.

Patients who are deemed eligible will be administered amifampridine phosphate for Day 0 at the study site, by the study personnel, and have the assessments/procedures listed below completed, in relation to the time of receiving study medication on Day 0, before randomization.

- Confirmation of Inclusion/Exclusion criteria;
- Assessment of AEs/SAEs;
- Abbreviated physical exam with weight;
- Vital signs (seated position), including SBP, DBP, heart rate, respiration, and body temperature;
- Clinical laboratory tests;
- Urine pregnancy test in females of childbearing potential only;
- Concomitant medications;
- IP accountability;
- Efficacy assessments, including:
 - MFM 20 or 32;
 - SGI (patient/parent/guardian/caregiver);
 - CGI-S;
 - CGI-I; and
 - Slurp test (optional).

Assessment	Start Time After Dose* (\pm 10 minutes unless otherwise specified)
SGI	40 minutes
MFM 20 or 32	after SGI
Slurp test, CGI-S and CGI-I	At end of assessments

*Administration of medication represents Time 0 (minutes)

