The site pharmacy will dispense bottles containing blinded amifampridine phosphate or placebo tablets, depending on the patient's Treatment Sequence assignment, for daily outpatient administration for 7 days (Days 1-7). Administration of blinded study medication will begin with the next scheduled dose following the Day 0 baseline assessment on open-label medication. (see Section 13.3).

13.3 Period 1

Administration will be continued on an outpatient basis for a total of 7 days (Days 1-7).

On Day 8 (+1) patients will be given a dose of the same study medication as the previous 7 days by the study personnel, at the site, so that the assessments/procedures listed below will be completed in relation to the time of study medication dosing.

- Assessment of AEs/SAEs;
- Abbreviated physical exam with weight;
- Vital signs (seated position), including SBP, DBP, heart rate, respiration, and body temperature;
- Clinical laboratory tests;
- Concomitant medications;
- IP accountability;
- Efficacy assessments, including:
 - MFM 20 or 32;
 - SGI (patient/parent/guardian/caregiver);
 - Stimulated Single fiber EMG (optional);
 - CGI-S;
 - CGI-I; and

- Slurp test (optional).

Assessment	Start Time After Dose* (± 10 minutes unless otherwise specified)
SGI	40 minutes
MFM 20 or 32	after SGI
Stimulated Single fiber EMG	after MFM
Slurp test, CGI-S and CGI-I	At end of assessments

*Administration of medication represents Time 0 (minutes)

If the stimulated single fiber EMG (optional assessment) is not to be performed, then the slurp test (also optional), CGI-S and CGI-I assessments should be done following completion of the MFM.

Open-label amifampridine phosphate will be dispensed at the Day 8 visit for administration during the stabilization period, starting with the next scheduled dose after Day 8 assessments (see Section 13.4).

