13.4 Re-stabilization Period

Patients will return to their prior open-label amifampridine phosphate dose established in the run-in phase for 2 weeks, Day 9 through Day 21.

Patients will report to the study site on Day 21 (+1 day) and have the assessments/procedures listed below completed.

- Assessment of AEs/SAEs;
- Abbreviated physical exam with weight;
- Vital signs (seated position), including SBP, DBP, heart rate, respiration, and body temperature;
- Urine pregnancy test in females of childbearing potential only;
- Concomitant medications;
- IP accountability;
- Efficacy assessments, including:
 - MFM 20 or 32;

- SGI (patient/parent/guardian/caregiver);
- CGI-S;
- CGI-I; and
- Slurp test (optional).

Assessment	Start Time After Dose* (\pm 10 minutes unless otherwise specified)
SGI	40 minutes
MFM 20 or 32	after SGI
Slurp test, CGI-S and CGI-I	At end of assessments

*Administration of medication represents Time 0 (minutes)

A The slurp test (optional), CGI-S and CGI-I assessments should be done following completion of the MFM.

The site will dispense bottles containing amifampridine phosphate or placebo tablets, depending on the patient's Treatment Sequence assignment, for Period 2 (Days 22-28). Administration of blinded study medication will begin with the next scheduled dose after Day 21 assessments are completed (see Section 13.5).

13.5 Period 2

Patients will the blinded study medication they did not receive in Period 1. Administration will be continued on an outpatient basis for a total of 7 days (Days 22-28).

Patients will report to the study site on Day 29 (+1 day) and receive a dose of the same study medication they received for the previous 7 days, under the supervision of the study personnel, in order to time the following assessments/procedures in relation to the medication dose.

- Assessment of AEs/SAEs;
- Complete physical exam with weight;
- Vital signs (seated position), including SBP, DBP, heart rate, respiration, and body temperature;
- Standard resting 12-lead ECG;
- Clinical laboratory tests;

- Urine pregnancy test in females of childbearing potential only;
- Concomitant medications;
- IP accountability;
- Efficacy assessments, including:
 - MFM 20 or 32;
 - SGI (patient/parent/guardian/caregiver);
 - Stimulated single fiber EMG (optional);
 - CGI-S;
 - CGI-I; and
 - Slurp test (optional).

Assessment	Start Time After Dose* (± 10 minutes unless otherwise specified)
SGI	40 minutes
MFM 20 or 32	after SGI

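### When the optional single-fiber EMG is done, slurp and CGI at Days 8 and 29 are taken later after dose than at Days 0 and 21, and Section 10.3.3 disagrees with 10.7 on where the EMG goes

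*Protocol*

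**What the plan says.** The timing table in Protocol Section 10.7 starts the SGI 40 minutes (±10) after the in-clinic dose. The MFM follows, then "Stimulated Single fiber EMG after MFM", then slurp, CGI-S and CGI-I at the end. The Day 8 table (Section 13.3) and the Day 29 table (Section 13.5) give the same order. When SFEMG is omitted, slurp and CGI move up to follow the MFM: "If the stimulated single fiber EMG (optional assessment) is not to be performed, then the slurp test (also optional), CGI-S and CGI-I assessments" are then next in line.

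SFEMG is not scheduled at either period baseline. The Day 0 list and timing table in Section 13.2 do not contain it. For Day 21, Section 13.4 says: "The slurp test (optional), CGI-S and CGI-I assessments should be done following completion of the MFM".

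Section 10.3.3 has its own copy of the timing table, which reads "Simulated Single fiber EMG [^] after SGI". The MFM row above it has the same anchor.

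Section 10.3.3 and footnote d of Table 3 both say that efficacy assessments are made at standardised times relative to dosing.

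SAP Section 4.2.2 takes slurp change from baseline against Day 0 and Day 21, with no formal inference. It tests CGI-S and CGI-I with a rank-sum test and a Hodges-Lehmann estimate. SFEMG is summarised only.

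**The concern.** The same test should be read at the same point on the dose clock at baseline and at the end of the period. For slurp and CGI this holds if SFEMG is skipped. If SFEMG is done, its duration is inserted before slurp and CGI at Days 8 and 29 only. On placebo there is no drug effect to lose over that interval; on amifampridine there may be. The drug effect on these measures could therefore be understated in patients who have SFEMG. Because SFEMG is optional and not done at all sites (SAP Section 4.1.2), patients would also differ in when slurp and CGI are read.

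The 10.3.3 row raises a second, separate issue. As printed it lets a site do the needle test before the MFM, which is the main secondary efficacy measure.

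**Working it through.** The plan gives no figure of its own on this point, so the check has three parts: the visit orders side by side, the effect on the contrast, and an illustration of size.

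**1. Visit orders when SFEMG is done**

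| Visit | Source | Order |
|---|---|---|
| Day 0 | 13.2 | SGI (40 min), MFM, slurp/CGI |
| Day 8 | 13.3, 10.7 | SGI (40 min), MFM, SFEMG, slurp/CGI |
| Day 21 | 13.4 | SGI (40 min), MFM, slurp/CGI |
| Day 29 | 13.5, 10.7 | SGI (40 min), MFM, SFEMG, slurp/CGI |

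SGI comes first at a fixed time at all four visits, so its shift is zero. MFM keeps its place under 10.7, 13.3 and 13.5. Slurp and CGI are displaced at Days 8 and 29 by the SFEMG time, *d*. Without SFEMG, *d* = 0.

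**2. Effect on the treatment contrast**

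Let *E(t)* be the drug effect at time *t* after dose, *t0* the time of slurp/CGI at baseline, and *t0 + d* the time at the end of the period. Both baselines are taken on open-label drug.

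- Change on amifampridine: *E(t0 + d) − E(t0)*
- Change on placebo: *0 − E(t0)*
- Amifampridine minus placebo: *E(t0 + d)*

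The baseline term cancels. Comparing end-of-period values directly gives the same *E(t0 + d)*, so the result does not depend on whether CGI is analysed as values or as changes. Without SFEMG the contrast would be *E(t0)*. The cost is *E(t0) − E(t0 + d)*, which is attenuation if the effect is falling over that interval. The cancellation assumes that a patient has SFEMG in both periods or in neither.

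**3. Illustration of size**

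Inputs: half-life *h* of 1.8 h (Protocol Section 8.5) and 1.8 to 2.5 h (SAP Section 4.2.2). SFEMG duration is not in the documents, so *d* = 30 to 60 minutes is an assumption. One feature makes 30 minutes plausible. Section 10.7.4 says "Local anesthetic agent will be applied to the site of needle electrode" examination half an hour beforehand; if that is done only after the MFM, the wait alone adds 30 minutes.

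Fraction of drug level remaining after a post-peak delay: *f = 2^(−d/h)*.

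| *d* | *h* = 1.8 h | *h* = 2.5 h |
|---|---|---|
| 30 min | 0.825 (fall 18%) | 0.871 (fall 13%) |
| 60 min | 0.680 (fall 32%) | 0.758 (fall 24%) |

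The range is about 13% to 32%, and it applies only after the peak. Section 8.4.1 gives a time to peak of about 78 minutes with food, and dosing is generally with food. SGI starts at 40 minutes, which leaves 78 − 40 = 38 minutes before the fed peak. If SGI and MFM together finish within that time, part of the delay falls while the level is still rising, and the loss is smaller.

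**The case against.** The strongest reply is that little of importance is exposed. SFEMG is optional, and without it the order at Days 8 and 29 matches the baselines. Slurp is descriptive, and the protocol itself plans only summaries for CGI; the formal test appears in the SAP. CGI-S and CGI-I are global clinician ratings, and nothing in the documents shows that they follow plasma level over tens of minutes. All of this stands, and it keeps the point small.

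The 10.3.3 row also looks like an editing slip. The Amendment 4 log shows that when the patient video was removed, the SFEMG anchor became the SGI in this table and the MFM in the others. The remark under the 10.3.3 table, that slurp and CGI follow the MFM when SFEMG is skipped, fits SFEMG coming after the MFM. That makes it an error to correct; it is not evidence that any site did SFEMG first.

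Putting SFEMG last is a trade-off too, since SFEMG is then read further from the dose. It has no formal test, however, and the SAP Table 37 shell takes Screening as its baseline, so no match to Day 0 or Day 21 is lost.

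A reader might infer more than the documents support:
- That the crossover comparison is confounded or could give a false positive. Both periods share the schedule, and the likely direction is towards no effect.
- That the needle or the anesthetic interferes with slurp, MFM or CGI. The protocol describes application at the needle site only, and no passage shows such an effect.
- That the protocol standardises timing because the half-life is short. It gives no such reason; Section 8.5 links the half-life to withdrawal and reversibility.

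**Conclusion.** The point holds in a limited form. When SFEMG is done, slurp, CGI-S and CGI-I at Days 8 and 29 are read later after dose than at Days 0 and 21, which departs from the protocol's own statement on timing. The likely consequence is some attenuation of the amifampridine effect on CGI and slurp, with added variability between patients who have SFEMG and those who do not. The primary SGI is unaffected. MFM is exposed only if a site follows the 10.3.3 row literally.

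The size cannot be determined. The 13% to 32% figure is a fall in drug level under an assumed 30 to 60 minute delay wholly after the peak. It should not be read as a loss of treatment effect, because effect is not shown to be proportional to concentration and part of the delay may precede the fed peak. The statement that the contrast is not confounded assumes SFEMG is done in both periods or in neither. This is an inexpensive improvement and does not threaten the trial's main conclusion.

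**What to change.** Use one order in Protocol Sections 10.3.3, 10.7, 13.3, 13.5 and 13.6: SGI, MFM, slurp, CGI-S and CGI-I, then SFEMG last where it is done. Correct the SFEMG row in 10.3.3 to match. Section 13.6 lists SFEMG among the early discontinuation assessments without a timing table, so the order needs stating there. Days 8 and 29 then follow the same sequence as Days 0 and 21 whether or not SFEMG is done, and the sentence about what to do if SFEMG is skipped is no longer needed.

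The change adds no test and no visit time. Its cost is that SFEMG, which is summarised descriptively only, is recorded somewhat later after dose, equally in both periods. If reordering is no longer possible, record the actual assessment times and whether SFEMG was done at each visit, so that the effect on CGI and slurp can be examined.
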